2.2. Endpoints

Primary Endpoint:

The primary endpoint in this study is change in overall ocular comfort score from baseline at 30-Day follow-up. Subjective overall ocular comfort will be assessed at baseline, 14-Day and 30-Day follow-up using a Visual Analogue Scale (VAS) with continuous scale from 0 (extremely uncomfortable) to 100 (extremely comfortable)⁷.

Secondary endpoint:

The secondary endpoint in this study is change in overall quality of vision score from baseline at 30-Day follow-up. Change in quality of vision from baseline will be assessed using Visual Analogue Scale (VAS) with continuous scale from 0 (extremely uncomfortable) to 100 (extremely comfortable) at 30-Day follow-up⁷.

Other Exploratory Endpoints:

- Corneal Staining
- Subject's reported ocular symptoms
- Tear film break up time
- Slit lamp findings using FDA scale
- End of day ocular comfort
- Snellen best corrected distance visual acuity
- Subjective evaluation of symptom of dryness
- Adverse Events
- Number and reasons for discontinuation will be monitored.
- Change in overall quality of vision from baseline at 14-Day follow-up using VAS
- Change in overall ocular comfort from baseline at 14-Day follow-up using VAS
- PRO and MRD analysis

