5.2. Masking

Masking will be used to reduce potential bias. Due to the difference in shape of the marketed eye drops compared to the test eye drops, double masking is not possible. However, the subjects will be masked from the identity of the eye drops. The identity of the investigational products will be masked by over labeling the eye drop bottles with a label containing the study number, expiration date and the randomization codes. Investigators and clinical site personnel involved in the data collection will not be masked as to the identity of the investigational product.

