7.2. Detailed Study Procedures

VISIT 1

Aim for Visit 1 to occur in the afternoon (After 12 PM). The subjects must present to Visit 1 wearing their spectacles (if applicable). Subjects will be requested to bring their habitual artificial tears with them to the visit (if applicable).

	Visit 1: Screening			
Step	Procedure	Details		
1.1	Statement of Informed Consent	Each subject must read, understand, and sign the Statement of Informed Consent before being enrolled into the study. The Principal Investigator or his/her designee conducting the informed consent discussion must also sign the consent form. NOTE : The subject must be provided a signed copy of this document.		
1.2	Demographics	Record the subject's year of birth, age, gender, race, and ethnicity.		
1.3	Medical History and Concomitant Medications	Questions regarding the subject's medical history and concomitant medications.		
1.4	Artificial Tear Use	The subject will be asked about their artificial tear use		
1.5	Eligibility after Screening	All responses to Screening Inclusion Criteria questions must be answered "yes" and all responses to Exclusion Criteria must be answered "no" for the subject to be considered eligible. If subject is deemed to be ineligible after screening, proceed to Final Evaluation and complete Subject Disposition. Refraction and Biomicroscopy forms are not required.		

	Visit 1: Baseline			
Step	Procedure	Details		
1.6	Entrance Visual Acuity	Record the distance high contrast visual acuity to the nearest letter (OD, OS, and OU) with their habitual spectacle correction in place (or unaided if applicable).		
1.7	Baseline Subject Reported Ocular Symptoms	Subjects will respond to a verbal open- ended symptoms questionnaire.		
1.8	Baseline VAS	The subject will respond to the VAS questionnaire using the Kiosk portal.		
1.9	Baseline PRO questionnaires	The subject will complete the electronic questionnaires using the Kiosk portal.		
1.10	Tear Break up Time	Record the tear film stability (NIBUT), OD and OS, with a Medmont or other topographer.	NIBUT work aid (Appendix D)	
1.11	Slit Lamp Biomicroscopy	The FDA slit lamp classification scale will be used to grade the findings and determine eligibility.		

	Visit 1: Baseline			
Step	tep Procedure Details			

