1.24	Dispense	 The artificial tears will be dispensed for a 14 +/- 2 day dispensing period Dispense one bottle of artificial tears A patient instruction guide will be provided, and the subject will be instructed not to use other artificial tears during the dispensing period. Subjects will be scheduled for Visit 2 in 14 +/- 2 days. Subjects will be instructed to bring the dispensed bottle of artificial tears to the next visit. Subjects will be instructed not to use other artificial tears during the dispensing period. 		

VISIT 2

Aim for Visit 2 to occur in the afternoon (after 12 PM). The subjects must present to visit 2 wearing their habitual spectacles (if applicable) having used the study drop in both eyes as instructed.

Visit 2: Follow-up 1			
Step	Procedure	Details	
2.1	Adverse Events and Concomitant Medications Review	Review the subject's concomitant medications and record any changes from the previous study visit. Record any adverse events or medical history changes from the previous study visit.	
2.2	Artificial Tear Compliance	Confirm the subject used the drops as instructed and record the average and maximum number of drops used in OD and OS per day.	
2.3	Collection of study drops	This bottle will be collected by the site and discarded.	
2.4	Subject Reported Ocular Symptoms	Subjects will respond to a verbal open-ended symptoms questionnaire.	
2.5	VAS Questionnaire	The subject will respond to the VAS Questionnaire using the Kiosk portal.	
2.6	PRO Questionnaire	The subject will complete the electronic questionnaires using the Kiosk portal.	
2.7	Preference Question	The subject will complete the electronic preference questions using the Kiosk portal, if applicable.	
2.8	Visual Acuity	Record the distance high contrast visual acuity to the nearest letter (OD, OS, and OU) with their habitual spectacle correction in place (or unaided if applicable).	
2.9	Tear Break up Time	Record the tear film stability (NIBUT), OD and OS, with a Medmont or other topographer.	NIBUT work aid (Appendix D)
2.10	Slit Lamp Biomicroscopy	The FDA slit lamp classification scale will be used to grade the findings and determine eligibility. If the clearance of the fluorescein needs to be expedited, preservative-free saline may be instilled.	
2.11	Expanded Sodium Fluorescein Corneal Staining	Corneal Staining Assessment (FDA grading scale) will be assessed using a more detailed scale for internal purposes only.	
2.12	Exit Visual Acuity	Record the distance high contrast visual	

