	Visit 2: Follow-up 1			
Step	Procedure	Details		
		acuity to the nearest letter (OD, OS, and OU) with their habitual spectacle correction in place (or unaided if applicable).		
2.13	Continuance	For the subject to continue in the study, they must meet both of the following criteria: • Exit Visual acuity is 20/30 or better OD and OS • Subject willing to use the drop 3-4 times a day, or as		
2.14	Dispense	 needed (up to 6 times a day) OU until Visit 3. Dispense one bottle of artificial tears The subject will be instructed not to use other artificial tears during the dispensing period. Subjects will be scheduled for Visit 3 to ensure the visit is completed 28 to 32 days after Visit 1. Subjects will be instructed to bring the dispensed bottle of artificial tears to the next visit. 		

VISIT 3

Aim for Visit 3 to occur in the afternoon (after 12 PM). The subjects must present to Visit 3 wearing their habitual spectacles (if applicable) having used the study drop in both eyes as instructed.

	Visit 3: Follow-up 2			
Step	tep Procedure Details			
3.1	Adverse Events and Concomitant Medications Review	Review the subject's concomitant medications and record any changes from the previous study visit. Record any adverse events or medical history changes from the previous study visit.		
3.2	Artificial Tear Compliance	Confirm the subject used the drops as instructed and record the average and maximum number of drops used in OD and OS per day.		
3.3	Collection of study drops	This bottle will be collected by the site and discarded.		
3.4	Subject Reported Ocular Symptoms	Subjects will respond to a verbal open-ended symptoms questionnaire.		
3.5	VAS Questionnaire	The subject will respond to the VAS Questionnaire using the Kiosk portal.		
3.6	PRO Questionnaire	The subject will complete the electronic questionnaires using the Kiosk portal.		
3.7	Preference Question	The subject will complete the electronic preference questions using the Kiosk portal, if applicable.		
3.8	Entrance Visual Acuity	Record the distance high contrast visual acuity to the nearest letter (OD, OS, and OU) with their habitual spectacle correction in place (or unaided if applicable).		

	Visit 3: Follow-up 2		
Step	Procedure	Procedure Details	
3.9	Tear Break up Time	Record the tear film stability (NIBUT), OD and OS, with a Medmont or other topographer.	NIBUT work aid (Appendix D)

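### At both follow-up visits, including the Day 30 primary time point, the kiosk VAS comes only after unmasked site staff have gone through adverse events, drop use and symptoms with the subject

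*Combined protocol and SAP*

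**What the plan says.** Section 2.2 defines the endpoint: "The primary endpoint in this study is change in overall ocular comfort score from baseline at 30-Day follow-up". It is a subject-rated 0-100 visual analogue scale. The secondary endpoint, quality of vision at Day 30, is also a VAS score.

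Section 7.2 numbers the Visit 3 procedures in this order:

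- 3.1, adverse event and medication review: "Record any adverse events or medical history changes from the previous study visit".
- 3.2, drop use: "Confirm the subject used the drops as instructed and record the average and maximum number of drops used in OD and OS per day".
- Bottle handed back to the site (3.3).
- 3.4, symptoms: "Subjects will respond to a verbal open-ended symptoms questionnaire".
- 3.5, the rating: "The subject will respond to the VAS Questionnaire using the Kiosk portal".

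Visit 2 has the same order in steps 2.1 to 2.5.

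On masking, section 5.2 says of subjects: "However, the subjects will be masked from the identity of the eye drops". Of staff it says: "Investigators and clinical site personnel involved in the data collection will not be masked as to the identity of the investigational product". Sections 4.2 and 5.2 explain that double masking is not possible because the droppers differ in shape.

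At Visit 1 the order differs in content. Medical history (1.3), tear use (1.4: "The subject will be asked about their artificial tear use") and the symptom questionnaire (1.7) come before the baseline VAS (1.8). Randomization is step 1.15. Table 4 marks adverse event review and compliance for Visits 2 and 3 only.

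**The concern.** In a trial where only the subject is masked, a subjective rating is best taken before the subject talks with anyone who knows the arm. Here the conversation comes first, and it covers the topics closest to the rating: problems since the last visit, how much drop was needed, and current symptoms. The kiosk protects the entry of the score. It does not protect against what was said a few minutes earlier.

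If staff follow up answers, reassure or phrase questions differently for the two products, even without intending to, the comfort score can move differently in the two arms. In a non-inferiority trial a shift toward Test makes a false claim of non-inferiority more likely, and a shift against Test costs power. No readable text requires steps 3.1 to 3.4 to come before the VAS, so the protocol appears to gain nothing in return for the exposure.

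**Working it through.** **1. Order against knowledge of assignment**

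| VAS | Comes after | Could staff know the arm? | Role |
|---|---|---|---|
| Visit 1, step 1.8 | History, tear use, symptom questionnaire | No; randomization is 1.15 | Baseline |
| Visit 2, step 2.5 | Adverse events, drop use, bottle, symptom questionnaire | Yes (5.2) | Exploratory, Day 14 |
| Visit 3, step 3.5 | Adverse events, drop use, bottle, symptom questionnaire | Yes (5.2) | Primary and secondary, Day 30 |

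**2. What cancels and what does not**

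Let c be the effect of the preceding conversation on the follow-up score that is common to both arms, and let d be the extra effect in the Test arm. The Test minus Control difference in mean change then contains (c + d) - c = d. The common part drops out. The part that differs by arm stays. Since d can arise only after assignment, subtracting the baseline score, or adjusting for it in the Plan A model, does not remove it.

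**3. The plan's own sample size, reproduced**

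Inputs from section 14.2: margin -20, true difference 0, power 90%, one-sided 0.025, SD 30.

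- Noncentral t: 49 per arm, as in Table 9.
- Wilcoxon: 49 × π/3 = 51.3, rounded up to 52 per arm, as in Table 10.
- 10% dropout: 52 / 0.90 = 57.8, rounded up to 58 per arm, 116 in total.

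These figures agree with the plan, and the reordering does not affect them.

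**4. Illustration of a differential shift**

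The documents give no value for d. The shifts of 2 and 4 points are assumptions, as is the use of 52 evaluable subjects per arm.

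- SE = 30 × √(2/52) = 5.88.
- Degrees of freedom = 2 × 52 - 2 = 102, so the critical t is 1.983.
- If the true difference is exactly -20 and the estimate is shifted by d toward Test, P(lower 95% limit above -20) = P(T > 1.983), where T is noncentral t with 102 degrees of freedom and noncentrality d/SE.

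| d (points) | d/SE at SD 30 | One-sided error, SD 30 | Range, SD 35 to SD 25 |
|---|---|---|---|
| 0 | 0 | 2.5% | 2.5% |
| 2 | 0.34 | 5.2% | 4.7% to 6.0% |
| 4 | 0.68 | 9.9% | 8.3% to 12.5% |

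At the planning difference of 0 with SD 30, power is about 92%. A 2- or 4-point shift toward Test raises it to about 96% or 98%. The same shifts against Test lower it to about 86% or 77%.

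**The case against.** There is a serious case on the other side, and several parts of it stand.

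- **The priming is balanced.** The symptom questionnaire directly precedes the VAS at baseline and at both follow-ups, in the same order in both arms. This stands for common priming. It does not answer influence that differs by arm.
- **The text does not describe probing.** Steps 3.1 and 3.2 review and record, and step 3.4 is a questionnaire. Reassurance or a different tone by arm is conjecture. This stands: what is established is an opportunity for influence. The protocol also does not name the interviewer; site staff is the natural reading.
- **Protections exist.** Subjects are masked by over-labelling, and they enter the score themselves. Both lower the likely size. Neither acts on the preceding conversation.
- **Reordering removes only part of the contact.** By Visit 3 the subject has already been observed instilling the drop, been interviewed and been instructed at Visit 1 after randomization, and has attended Visit 2. This stands.
- **Instructions may exist elsewhere.** Appendix A (questionnaires) and Appendix E (symptom and patient-reported outcome instructions) are not readable in the public file. Rules on wording, privacy or order may be there.
- **The error rates need Test to be truly 20 points worse.** At a true difference of 0, a shift toward Test only helps reach a correct conclusion. This also stands, and it is why the figures are illustrative.

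A reader might also infer that the rating is exposed in this way at every visit. The documents do not support that. Visit 1 has no adverse event or compliance review, and its baseline VAS is taken before any assignment exists.

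**Conclusion.** The point holds as an avoidable design exposure at Visits 2 and 3. It matters most at Visit 3, which supplies the primary and secondary endpoints; the Visit 2 scores are exploratory. The step order and the absence of staff masking are plain in sections 7.2 and 5.2, and nothing readable requires that order.

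The size is unknown. An error of about 5.2% or 9.9% in place of 2.5% rests on assumed shifts of 2 or 4 points toward Test, SD 30, 52 per arm and a true difference at the margin. For scale, 4 points is one fifth of the margin.

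It would be tempting to conclude that the comfort comparison is biased, or that the plan contains an error. Neither follows. Bias arises only if staff deal with the two arms differently, and the documents give no evidence that they would. The reason to act is that the protection is nearly free.

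**What to change.** In section 7.2:

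- **Visit 3:** make the kiosk VAS (3.5) the first procedure, followed by the other kiosk questionnaires (3.6, 3.7), and then steps 3.1 to 3.4.
- **Visit 2:** do the same with 2.5, then 2.6 and 2.7, ahead of 2.1 to 2.4.
- **Visit 1:** put the baseline VAS (1.8) before the symptom questionnaire (1.7), so that the baseline and follow-up ratings stand in the same relation to that interview. History and tear use (1.3, 1.4) would still come earlier because they serve screening.
- **Table 4:** align the row order with the revised steps.
- **Appendices A and E:** check for any rule on how the VAS or symptom questionnaire is administered, and make it consistent with the new order.

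The cost is editorial, plus site training on the new sequence. No procedure, subject or visit time is added, safety questioning moves only within the same visit, and the sample size stays at 116. Exposure to unmasked staff at earlier visits remains, and the study report should say so.

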7.3. Unscheduled Visits

If, during the investigation, a subject requires an unscheduled visit to the clinical site, the following information will be collected, as appropriate:

• Chief complaint prompting the visit. If the reason is an adverse event, the applicable eCRF for the adverse event must be completed and the subject record completed as appropriate.

- Date and time of the visit and all procedures completed at the unscheduled visit.
- Review of adverse events and concomitant medications.
- Documentation of any test article dispensed or collected from the subject, if applicable.
- Slit lamp findings (using the Slit Lamp Classification Scale).

If the Investigator withdraws a subject from the study, the final study visit case report forms must be completed indicating the reason(s) why the subject was withdrawn. The subject record must be completed documenting the date and primary reason for withdrawal and the study CRA notified.

Any ocular and non-ocular Adverse Events that are ongoing at the time of the study visit will be followed by the Investigator, within licensure, until they have resolved, returned to pre-treatment status, stabilized, or been satisfactorily explained. If further treatment i.e., beyond licensure is required, the subject will be referred to the appropriate health care provider.

	Unscheduled Visit		
Step	Procedure	Details	
U.1	Reason for unscheduled visit	Indicate if the only reason for the visit is that the subject requires additional test eye drops. If the reason is other than resupply of previously dispensed eye drops, specify the reason for the visit.	
U.2	Chief Complaints (if applicable)	Record the subject's chief complaints for reasons for the unscheduled visit.	
U.3	Adverse Events and Concomitant Medications Review (if applicable)	Review any changes to the subject's medical history or concomitant medications from the previous study visit. Record any changes, and any adverse events.	
U.4	Entrance Visual Acuity (if applicable)	Record the entrance distance visual acuity (OD, OS and OU) to the nearest letter.	
U.5	Subjective Sphero- cylindrical Refraction (if applicable)	Perform bare-eye subjective spherocylindrical refraction with a phoropter (adopt the maximum plus to maximum visual acuity (MPMVA) approach and use the duo-chrome test for binocular balancing) and record the best corrected distance visual acuity to the nearest letter (OD, OS).	
U.6	Slit Lamp Biomicroscopy (if applicable)	FDA Slit Lamp Classification Scale will be used to grade the findings. If the clearance of the fluorescein needs to be expedited, preservative-free saline may be instilled.	
U.7	Dispensing (if applicable)	If the subject requires additional test eye drops to complete the study period and is eligible to do so, provide additional eye drops per the dispensing instructions given in the detailed study procedures.	
U.8	Exit Visual Acuity (if applicable)	Record the subject's exit distance visual acuity (OD, OS, and OU) to the nearest letter.	

The following information will be collected during an unscheduled visit.

NOTE: If the only reason for the unscheduled visit is that the subject requires additional test articles, only the dispensing information needs to be recorded.

7.4. Laboratory Procedures

Not Applicable

8. SUBJECTS COMPLETION/WITHDRAWAL

8.1. Completion Criteria

Subjects are considered to have completed the study if they:

- provided informed consent.
- they are eligible.
- Completed all study visits
- Not have withdrawn/ discontinued from the study for any reason described in section 4.2.

8.2. Withdrawal/Discontinuation from the Study

A subject will be withdrawn from the study for any of the following reasons:

- Subject withdrawal of consent.
- Subject not compliant to protocol including drop usage schedule
- Subject lost to follow-up.
- Subject no longer meets eligibility criteria (e.g. the subject becomes pregnant).
- Subject develops significant or serious adverse events necessitating discontinuation of study eyedrops
- Subjects who have experienced a Corneal Infiltrative Event (CIE).
- Investigator's clinical judgment regarding the subject safety reasons (that it is in the best interest of the subject to stop treatment).
- Subject deemed incapable of dispensing the drops safely and effectively (Based on investigator's judgment.

For discontinued subjects, the Investigator will:

- Complete the current visit (scheduled or unscheduled).
- Complete the Final Evaluation, indicating the reason that the subject was discontinued from the study.
- Record the spherocylindrical refraction with best corrected distance visual acuity.
- Collect used test article(s) (used or brought to the visit) from the subject and discard them, unless otherwise stated in section 7.2.
- Collect all unused test article(s) from the subject.
- Make arrangements for subject care, if needed, due to their study participation

Additional subjects will be enrolled if a subject discontinues from the study prematurely (within the enrollment window specified by the sponsor).

In cases where a subject is lost to follow-up, every possible effort must be made to contact the subject and determine the reason for discontinuation/withdrawal. The measures taken to follow up must be documented including two written attempts and a certified letter (or equivalent) as the final attempt.

9. PRE-STUDY AND CONCOMITANT INTERVENTION/MEDICATION

Concomitant medications will be documented during screening and updated during the study. Disallowed medications for this study include: Current habitual use of Prescription-only medicines for Dry Eye Diseases or ocular discomfort, ocular steroids, or any medications (either prescription-only or OTC) that would interfere with the clinical study (at the discretion of the investigator).

Concomitant therapies that are disallowed include: Current habitual use of Prescription-only medications for dry eye diseases and ocular discomfort, ocular steroids, or any medication (RX or OTC) that would interfere with the clinical study (at the discretion of the investigator).

9.1. Systemic Medications

Certain systemic medications are known to have a higher likelihood to disrupt the tear film.

A summary of disallowed systemic medications is shown in Table 5: Systemic medications list. Subjects with a history of taking these medications will be allowed to enroll only if:

• The subject was taking the medication on a temporary basis and ceased taking that medication at least 4 weeks prior to signing the informed consent (this is considered sufficient time for the medication to have left the body prior to enrollment).

Subjects with a history of taking medications listed in Table 5 on a long-term, routine basis will not be allowed to participate in the study.

Class of Drug	Common Indication(s)	Common Examples
Anticholinergics	Irritable bowel syndrome, Parkinson's disease, peptic ulcer, cystitis, nasal congestion, cold symptoms, overactive bladder, COPD	Bentyl, Spiriva, Atrovent, Hyosyne, Levsin, Symax Fastab, Symax SL, Homax SL, Cogentin, Transderm Scop, etc.,
Oral Phenothiazines	Antipsychotic disorders (schizophrenia, mania)	Compazine, Mellarill, Thorazine, Phenagran, etc
Oral Retinoids	Cystic acne	Isotretinoin
Corticosteroids	Arthritis, colitis, asthma, bronchitis, allergic or inflammatory conditions	Cortisone, Prednisone, Hydrocortisone, Medrol, Kenalog etc.,
Oral Tetracycline	Urinary Tract Infection, acne, chlamydia, gonorrhea	Sumcyin, Acitsite, Achromycin V, etc.

Table 5: Systemic medications list

Examples of disallowed systemic antihistamines are given below. Subjects with a history of taking systemic antihistamines will be allowed to enroll only if:

• They have taken antihistamines continuously for at least 2 weeks with no residual symptoms as per investigator's discretion

Or:

They stopped taking the medication for at least 2 weeks prior to enrollment.

Table 6: Disallowed	systemic antihistamines
---------------------	-------------------------

Class of Drug	Common Indication(s)	Common Examples
Oral	Allergic rhinitis, allergic	Hydroxyzine, Promethagan,
antihistamines	dermatologic reaction, sinusitis,	Phenadoz, Vistaril, Claritin, Zyrtec,
	allergic conjunctivitis, nausea, motion	stepro, Astelin, Optivar, Allegra,
	sickness etc.	Benadryl, etc.

